3 COHORT 1 ANALYSIS

Cohort 1 subject data will be analysed and evaluated once █ Cohort 1 subjects have completed █ (or discontinued prior to █). The data will be cleaned and soft locked at this point for analysis. The following Cohort 1 data outputs will be provided (see also Appendix 1 for a full list of outputs):

- All listings detailed within this SAP apart from those relating to study drug dispensing, study drug return, study drug [REDACTED], [REDACTED] levels, local laboratory results and physical examination.
- By subject line plots detailed within sections: 5.1.1 Muscle Function, 5.1.2 Clinician/Caregiver Symptom Scales, 5.1.3 Cognitive and Neurodevelopment and 5.1.4.1 DXA scan.
- Summaries of the number and percentage of subjects experiencing “treatment period” treatment-emergent adverse events (TEAEs), “post treatment period” TEAEs, all TEAEs and separately non-treatment-emergent adverse events (NTEAEs) will be presented by system organ class (SOC) and preferred term (PT).

3.1 Ad Hoc Cohort 1 Analysis

It was planned that on review of the above specified Cohort 1 data outputs, additional outputs could be produced on Cohort 1 data if considered useful to interpretation of the data. Following review of the Cohort 1 outputs specified in

Section 3, a set of ad hoc outputs were requested to support the [REDACTED] [REDACTED]. The full list of ad hoc Cohort 1 outputs requested is given in Appendix 2. As these are ad hoc outputs, no accompanying table, listing and figure shells are provided. The layout and footnotes for each output were adapted from shells for equivalent outputs in this SAP. Sections 3.1.1 to 3.1.6 provide the full specification that was followed for the ad hoc Cohort 1 analyses. All of the ad hoc Cohort 1 outputs were produced in line with this specification following discussion and agreement with AMO Pharma Ltd.

3.1.1 [REDACTED] and [REDACTED] Comparisons for Selected Efficacy Endpoints

The mixed effect model repeated measures (MMRM) described in sections 5.1.1.2, 5.1.1.3, 5.1.1.5, 5.1.2.2, 5.1.2.3 will be adapted for selected endpoints to allow comparison of observed values at [REDACTED] to [REDACTED], as well as [REDACTED] to [REDACTED]. The model will be updated so that the dependent variable is the observed values at all scheduled visits for the endpoint from [REDACTED] to [REDACTED]. Visit will be kept as the only fixed effect. Contrasts will be obtained for the comparison of [REDACTED] to [REDACTED], as well as [REDACTED] to [REDACTED].

For each of these comparisons, the results to be presented will include the difference in adjusted Least Squares (LS) Means, together with the associated standard error (SE), 95% confidence intervals (CIs) and 2-sided p-values. In addition, the observed mean absolute change and observed mean percentage change for each comparison will be presented. If the assumptions of normality do not appear to hold for any endpoint, the observed median absolute change and observed median percentage change will also be presented as an alternative measure of the 'average' values. Finally, the Cohen's d value for each comparison will be presented.

In addition to performing the adapted MMRM analyses for the endpoints in the referenced sections, similar analyses will also be performed for the Clinical Global Impression - Improvement scale (CGI-I) and the Ohio State University (OSU) CGI-I. There are no MMRM analyses planned in this SAP for these endpoints and therefore the model will be adapted from the analysis of relaxation time in section 5.1.1.2 (CGI-I) and the analysis of total clinician-completed domain specific causes for concern VAS in section 5.1.2.2 (OSU CGI-I). As CGI-I and OSU CGI-I are not collected at [REDACTED], only the comparison between [REDACTED] and [REDACTED] will be performed.

Furthermore, the Peabody picture vocabulary test age-based standard score will also be analysed using an MMRM model as described above. No MMRM analysis is planned in this SAP for this endpoint and so the model will be adapted from the analysis of relaxation time in section 5.1.1.2. Observed scores at [REDACTED] and [REDACTED] will be included in the model.

Finally, a comparison from [REDACTED] to [REDACTED] in the Dual-energy X-ray Absorptiometry (DXA) – arms will be performed. As this endpoint is only collected at [REDACTED] and [REDACTED] the ANCOVA described in section 5.1.4.1 will be applied, with the removal of the dose group fixed effect.

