2.2 Study Design

This is a single-blind, [REDACTED] study in adolescent and adult subjects with congenital or juvenile-onset type 1 myotonic dystrophy.

Approximately 16 subjects in total are planned to be enrolled and receive active treatment.

Participation for individual subjects will consist of an initial Screening of up to [REDACTED] (minimum of [REDACTED]) followed by a [REDACTED] treatment phase. After this, subjects in Cohort 1 will be treated with single-blinded 1000mg tideglusib once daily orally for 12 weeks and Cohort 2 will be treated with single-blinded 400mg tideglusib once daily orally for 12 weeks. A follow up visit will take place approximately [REDACTED] after the end of treatment visit.

Once [REDACTED] out of the [REDACTED] subjects from Cohort 1, who have received active treatment with [REDACTED] of tideglusib, have completed active treatment or discontinued from the study [REDACTED] the Data Safety Monitoring Committee (DSMC) will meet to review the available data and a recommendation will be made to the Sponsor whether Cohort 2 should be initiated. [REDACTED]

Active dosing of Cohort 2 will only start when the [REDACTED] tideglusib. No screening will take place for Cohort 2 until after the recommendation has been made from the DSMC, to the Sponsor, on if Cohort 2 should be initiated.

If the decision is made to enrol all Cohort 2 subjects on the [REDACTED] dose then the summaries and analyses described in this SAP will be updated to analyse all subjects from cohorts 1 and 2 as a single dose group in the final analysis at the end of the study.

All outputs specified in this SAP will be produced for the final analysis of the combined Cohort 1 and Cohort 2 subject data. The exceptions to this are the by subject line plots detailed within Sections 5.1.1, 5.1.2, 5.1.3 and 5.1.4.1, as well as the ad hoc Cohort 1 outputs specified in section 3.1. These specific outputs will only be produced for the Cohort 1 analysis (see Sections 3 and 3.1) and will be included in the final study report as a separate set of Cohort 1 specific analyses on this data cut. They will not be reproduced on subsequent data unless, at the end of the study, it is considered beneficial to produce these again as part of ad hoc analyses.

See protocol section 8.3 for full detail of the study design.

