5.1.4 Biomarker

5.1.4.1 Dual-energy X-ray Absorptiometry (DXA) Whole Body Scan of Lean Muscle Mass

An ANCOVA will be fitted to the change from baseline to end of treatment in the DXA scan total lean muscle mass (g). The model will be fitted and results presented as described in section 5.1.2.1 for CGI-S.

The observed muscle mass and corresponding change from baseline to end of treatment will be summarised separately for the arms, the legs and the total muscle mass. The observed muscle mass for the arms, the legs and total muscle mass will also be presented over time ([] and []) using by subject line plots by dose group. In addition, line plots will present the adjusted LS mean changes from baseline to end of treatment and SEs, as estimated by the ANCOVA, by dose group for the DXA scan total lean muscle mass (g).

Lean muscle mass data will be listed.

5.1.4.2 []

[]
[] . []
[]

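### The Cohort 1 ad hoc models cover nine variables picked after the efficacy data were reviewed, with p-values and Cohen's d, no visible selection rule, and no matching contrast for eight planned endpoints

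*SAP*

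**What the plan says.** SAP Section 3 sets out the first round of Cohort 1 outputs. It includes nearly all listings, with those for every clinical efficacy instrument, and the following figures: "By subject line plots detailed within sections: 5.1.1 Muscle Function, 5.1.2 Clinician/Caregiver Symptom Scales, 5.1.3 Cognitive and Neurodevelopment and 5.1.4.1 DXA scan".

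SAP 3.1 describes the second round. It records a plan that, once the first round had been reviewed, "additional outputs could be produced on Cohort 1 data if considered useful to interpretation of the data". The order of events is explicit: "Following review of the Cohort 1 outputs specified in" Section 3, "a set of ad hoc outputs were requested to support the" (the purpose is then redacted). The models "will be adapted for selected endpoints to allow comparison of observed values" between visits. For each comparison, 3.1.1 asks for the difference in LS means with SE, 95% CI and two-sided p-value, and for Cohen's d. SAP 3.1.2 adds exact McNemar p-values for CGI-I and OSU CGI-I responders. I found no selection rule, no multiplicity statement and no description of the p-values as descriptive.

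For DXA, 3.1.1 analyses arms lean mass: "the ANCOVA described in section 5.1.4.1 will be applied, with the removal of the dose group fixed effect". SAP 5.1.4.1 specifies that ANCOVA for total lean mass only; arms and legs are summarised.

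SAP 2.2 says the Cohort 1 outputs "will be included in the final study report as a separate set of Cohort 1 specific analyses on this data cut". They are not repeated on later data unless that is thought beneficial. The same section says all other SAP outputs will be produced at the final combined analysis.

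**The concern.** When endpoints are chosen for modelling after subject-level results have been seen, the estimates and p-values for those endpoints no longer have their usual meaning. The choice may have followed the data. The ad hoc label tells the reader when the choice was made. It does not tell the reader what the same analysis would have given for the endpoints not chosen.

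This matters more here than in a controlled trial. There is no parallel placebo arm, the sponsor and site know the treatment at every point (protocol 9.3), and Cohort 1 has eight subjects. The Cohort 1 set will stand as its own block in the final report, and its Cohen's d values are what a reader would carry forward to the design of a later study.

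**Working it through.** **Step 1. Count the modelled variables.** The left column is SAP 5.1.1 to 5.1.4; the right is SAP 3.1.1 with the Appendix 2 tables.

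| Variable modelled in Section 5 | Cohort 1 ad hoc model |
|---|---|
| 10 m walk/run, preferred speed | no |
| Grip strength, dominant hand | no |
| Relaxation time, dominant hand | yes |
| FVC | yes |
| Actigraphy, 3-minute bouts | no |
| NHPT, dominant arm | yes |
| CGI-S | no |
| CGI-I | yes |
| Clinician domain VAS total | yes |
| Top 3 total, caregiver | yes |
| Top 3 total, subject | no |
| OARS total impairment mean | no |
| OSU CGI-S | no |
| OSU CGI-I | yes |
| PPVT age-based standard score | yes |
| DXA total lean mass | no (arms instead) |

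Eight of 16 are covered and eight are not. DXA arms makes nine ad hoc models. One member of a planned pair is taken four times: relaxation time without grip strength, caregiver without subject Top 3, CGI-I without CGI-S, OSU CGI-I without OSU CGI-S. No reason is given.

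Two points affect the count. SAP 3.1.1 says no MMRM is planned for CGI-I or OSU CGI-I, but 5.1.2.1 and 5.1.3.2 plan one for each. Taking 3.1.1 literally gives 14 modelled variables, 6 covered and 8 omitted. Also, Appendix 2 titles Table 14.2.11.1_AH1a as the OSU improvement scale but abbreviates it OSU CGI-S; I followed 3.1.1 and counted it as OSU CGI-I.

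**Step 2. Count the p-values.** Five variables (relaxation time, FVC, NHPT, clinician VAS, caregiver Top 3) with two contrasts each give 10. CGI-I and OSU CGI-I give one each, 2. PPVT gives 1 or 2 (visits redacted). DXA arms gives 1 and the McNemar tests give 2. The total is 16 or 17. If they were independent and each read at 0.05, the chance of at least one false positive would be 1 − 0.95^16 = 0.56 or 1 − 0.95^17 = 0.58. The tests are correlated, so this is only a rough guide.

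**Step 3. Worst-case size of the selection effect.** The plan gives no effect size, SD or power figure to reproduce, so this is an illustration on stated assumptions: 16 normally distributed endpoints with no true effect, n=8 (SAP 2.4), equal correlation between endpoints, d = mean change / SD of change, and the eight most favourable d values shown. Simulation with 40,000 runs:

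| Correlation | Mean d, selected eight | All eight selected favour drug | All of eight prespecified favour drug |
|---|---|---|---|
| 0 | about 0.30 | 60% | 0.4% |
| 0.3 | 0.26 | 54% | 5% |
| 0.5 | 0.22 | 53% | 11% |

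The mean d over all 16 endpoints is 0 in each case. The simulation does not reproduce the real set exactly: that set has nine variables, one of them outside the 16, and five carry two contrasts.

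**The case against.** Several points on the other side stand.

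- **Motive.** A reader might infer that the sponsor picked the endpoints that looked good. The documents do not support that. The purpose of the request is redacted, and a neutral basis for the choice may lie there.
- **Suppression.** A reader might infer that the other endpoints disappear. They do not. All eight are in the Cohort 1 listings. Section 5 specifies by-subject plots for five of them (walk, grip, actigraphy, subject Top 3, DXA total). All 16 models are due at the final analysis by dose group, so the 1000 mg change from baseline will be reported for each, unless the conditional single-dose pooling in SAP 2.2 applies.
- **Run-in comparison.** It is tempting to say that the run-in versus treatment comparison exists only for the chosen endpoints. The visits in the 3.1.1 contrasts are redacted; only the McNemar test is described that way. Section 5 also summarises run-in change for walk, grip, CGI-S, both Top 3 scores, OARS and OSU CGI-S, and plots it beside the LS means for all of these except OARS.
- **DXA arms.** It is a named secondary endpoint (protocol 8.2) and was not invented after the fact. Only the model is new.
- **False positives.** Under the simulation, favourable p<0.05 rises from 2.5% to 5.0% of displayed tests, but this only divides the same false positives by 8 instead of 16. The chance of at least one favourable p<0.05 is about 26% at correlation 0.3 with or without the selection. Likewise the 54% should be set against eight prespecified endpoints, not against all 16 being favourable.

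The analyses are also openly labelled, were foreseen, and are itemised in Appendix 2, in an unpowered study whose primary objective is safety. None of this supplies a selection rule or the missing Cohort 1 contrasts.

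**Conclusion.** The point holds as a selective-reporting risk in a secondary, exploratory part of the report. Nine variables were chosen after data review and given p-values and Cohen's d with no visible rule. Eight of the 16 planned modelled variables have no matching Cohort 1 contrast, and DXA arms stands where DXA total was planned. The eight-of-16 figure rests on counting each modelled variable separately; counting DXA arms as covering DXA gives nine.

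If selection was entirely by result, effect sizes averaging about 0.2 to 0.3 could appear with no true effect, and uniformly favourable results would be weak evidence. That is an upper bound under the stated assumptions. It does not estimate what happened. The final analysis limits the harm but does not remove it, because the Cohort 1 block is reported separately. The primary safety objective is not affected.

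**What to change.** In SAP 3.1.1 and Appendix 2:

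1. Add the Cohort 1 contrasts for the eight omitted variables wherever the visit schedule allows, with one comparison where only two visits exist (as for DXA). For actigraphy, which has no planned run-in change, give the on-treatment contrast only.
2. Show DXA total and legs beside arms in the same table.
3. Mark which outputs were requested after data review, and state the selection rule if there was one.
4. Label every p-value in the set, including the McNemar tests, as post hoc, unadjusted and descriptive, and put the weight on estimates and 95% CIs. The outputs have already been produced, so labelling the p-values is sounder than deleting them.
5. While editing, reconcile the 3.1.1 statement on CGI-I and OSU CGI-I with 5.1.2.1 and 5.1.3.2, and correct the OSU abbreviation in Appendix 2.

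The cost is a few extra model runs and a longer table. Walk, grip, subject Top 3 and OARS already have MMRMs to adapt. CGI-S and OSU CGI-S are planned as ANCOVA and need the kind of adaptation already made for PPVT. Subject Top 3 ratings are made only where possible, so that row may rest on fewer than eight subjects.

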### **Clinician and caregiver rating scales of syndrome-specific symptoms**

### **10.2.7 Clinical Global Impressions Severity and Improvement**

The clinician administered Clinical Global Impressions of Severity (CGI-S) and Improvement (CGI-I) scale (Guy, 1976) will be performed in accordance with schedule of assessment (Table 1). The CGI rating scale permits a global evaluation of the subject's improvement over time and will be administered as detailed in the schedule of assessments.

The CGI-S is a 7-point Likert type scale that requires the clinician to rate the severity of the subject's illness at the time of assessment, relative to the clinician's past experience with subjects who have the same diagnosis. Considering total clinical experience, a subject is assessed on severity of illness at the time of rating 1, normal, not at all ill; 2, borderline ill; 3, mildly ill; 4, moderately ill; 5, markedly ill; 6, severely ill; or 7, extremely ill.

The CGI-I requires the clinician to rate how much the subject's illness has improved or worsened relative to a baseline state. A seven point Likert type scale is used from 1 = very much improved, 2 = much improved, 3 = minimally improved, 4 = no change, 5 = minimally worse, 6 = much worse, 7 = very much worse.

The CGI-I at Baseline █ should be rated against the CGI-S at Run-in █ For subsequent CGI-I ratings completed from Week █ onwards, the assessment should be compared against the CGI-S, done at Baseline █

In this study, a standard set of probes/prompts will be provided to the sites to assist the evaluator in eliciting commentary from the subject or their caregiver across each of the core domains and also on associated symptoms. Every effort will be made so that the same evaluator will also observe the subject at each visit to the clinic.

As part of the physician evaluation of the subject for the CGI-S and CGI-I ratings, if additional information is volunteered by the subject and/or caregiver which the physician feels supports the ratings, but is not captured elsewhere in the CRF, this information will be recorded in the source and captured within a comments field within the eCRF.

A copy of the CGI-S and CGI-I to be used in the study, along with instructions is included in Appendix D.

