Figure 14.2.3.1 Plot of Pulmonary Function Test over Time

Figure 14.2.4.1 Plot of Actigraphy over Time

Figure 14.2.5.1 Plot of Time Taken (Seconds) to Complete the Nine Hole Peg Test over Time

Figure 14.2.6.1 Plot of Clinical Global Impression over Time

Figure 14.2.7.1 Plot of Clinician-completed Domain Specific Causes for Concern VAS: Myotonic Dystrophy over Time

Figure 14.2.8.1 Plot of Subject Top Three Concerns VAS Total Score over Time

Figure 14.2.9.1 Plot of Caregiver Top Three Concerns VAS Total Score over Time

Figure 14.2.10.1 Plot of OSU Global Improvement Scale for Autism over Time

Figure 14.2.11.1 Plot of Peabody Picture Vocabulary Test over Time

Figure 14.2.12.1 Plot of DXA Scan (Body Composition - Lean Muscle Mass) over Time

APPENDIX 2

The following ad hoc Cohort 1 data outputs will be provided after soft lock of the Cohort 1 subjects as described in Section 3.1:

Tables:

- Table 14.2.2.2_AH1 Analysis of Relaxation Time (Seconds) for the Dominant Hand over Time
- Table 14.2.3.1_AH1 Analysis of FVC (litres) over Time
- Table 14.2.5.1_AH1 Analysis of the Time Taken (Seconds) to Complete the Nine Hole Peg Test for the Dominant Arm over Time
- Table 14.2.6.1_AH1a Analysis of Clinical Global Impression of Improvement Scale (CGI-I) over Time
- Table 14.2.6.1_AH1b Summary of Clinical Global Impression of Improvement Scale (CGI-I) - Number of Subjects with Improvement at Baseline and End of Treatment
- Table 14.2.7.1_AH1 Analysis of Clinician-completed Domain Specific Causes for Concern VAS Total Score (cm) over Time
- Table 14.2.9.1_AH1 Analysis of Caregiver Top Three Concerns VAS Total Score (cm) over Time
- Table 14.2.11.1_AH1a Analysis of OSU Global Improvement Scale for Autism (OSU CGI-S) over Time
- Table 14.2.11.1_AH1b Summary of OSU Global Improvement Scale for Autism (OSU CGI-I) - Number of Subjects with Improvement at Baseline and End of Treatment
- Table 14.2.12.1_AH1 Analysis of the Peabody Picture Vocabulary Test Age-Based Standard Score over Time
- Table 14.2.13.1_AH1 Analysis of Change from Baseline in the DXA Scan Arms Lean Muscle Mass (g) to End of Treatment

Figures:

- Figure 14.2.1.1_AH1 Scatter Plot of Time Taken (Seconds) to Complete 10-metre Walk/Run Test at Week █
- Figure 14.2.2.1_AH1a Bar Chart of Handgrip Myometry over Time – Mean Value +/- Standard Deviation
- Figure 14.2.2.1_AH1b Scatter Plot of Handgrip Myometry at Week █

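### On its natural reading, SAP 3.1.1 gives a percentage change for CGI-I and OSU CGI-I, two change ratings without a true zero, so the figure depends on arbitrary numbering

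*SAP*

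**What the plan says.** SAP 3.1.1 adapts the repeated-measures models to compare pairs of visits in Cohort 1. Besides the model contrasts it requires a mean absolute change, and it says that the "observed mean percentage change for each comparison will be presented". If normality looks doubtful, median versions of both are added.

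The same section then brings in two more scales: "similar analyses will also be performed for the Clinical Global Impression - Improvement scale (CGI-I) and the Ohio State University (OSU) CGI-I". It names the models to be adapted and keeps a single comparison, for the reason that begins "As CGI-I and OSU CGI-I are not collected at" (the visit label is redacted). It does not say that the percentage change is left out for these scales.

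Protocol 10.2.7 defines CGI-I as a rating of how much the illness "has improved or worsened relative to a baseline state", on seven points whose middle runs "3 = minimally improved, 4 = no change, 5 = minimally worse". Lower is better. The Baseline rating is made against CGI-S at Run-in, and later ratings against CGI-S at Baseline. Protocol 10.2.11 sets the same two references for the OSU scale and says it is rated in a similar way.

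SAP 5.1.2.1, the main analysis, compares the CGI-I means with 4. It plans neither a change from baseline nor a percentage for CGI-I. SAP 2.2 says the ad hoc Cohort 1 outputs go into the final study report.

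**The concern.** A percentage change is interpretable when zero means none of the quantity. That is true of seconds on the peg test, litres of FVC or centimetres on a VAS. It is not true of CGI-I. The scale starts at 1, its neutral point is 4, and each rating already expresses change from its own reference visit. The calculation takes the difference between two change ratings and divides it by the category number of the first. That number is a label and could equally have run the other way.

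What is at stake is how two tables in the final report are read: 14.2.6.1_AH1a for CGI-I and 14.2.11.1_AH1a for the OSU improvement scale (the latter's title carries the abbreviation for OSU CGI-S). A reader given a mean absolute change and a mean percentage change in the same table will expect them to agree in direction. Here they need not.

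**Working it through.** The plan states no figure to reproduce, so the check is direct arithmetic.

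**Inputs.** The coding is 1 to 7, with 4 as no change and lower better (Protocol 10.2.7). The planned Cohort 1 size is 8 (SAP 2.4). The two visits are taken as Baseline and End of Treatment. Their labels are redacted in 3.1.1, and the inference rests on the Appendix 2 title of the companion responder table, "Number of Subjects with Improvement at Baseline and End of Treatment". The arithmetic holds for any two visits with ratings.

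**Formula.** Percentage change = 100 × (later − earlier) / earlier. It is applied to the scale as numbered (x), reversed (8 − x) and centred on no change (x − 4).

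**Single subjects.**

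| Ratings | Absolute change | As numbered | Reversed | Centred on 4 |
|---|---|---|---|---|
| 2 then 4 | +2 | 100 × 2/2 = +100% | 6 then 4: 100 × (−2)/6 = −33.3% | −2 then 0: −100% |
| 4 then 2 | −2 | 100 × (−2)/4 = −50% | 4 then 6: 100 × 2/4 = +50% | 0 then −2: undefined |
| 6 then 4 | −2 | 100 × (−2)/6 = −33.3% | 2 then 4: 100 × 2/2 = +100% | 2 then 0: −100% |

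Reversing the scale changes only the sign of the absolute difference. It also changes the size of the percentage, here by a factor of three for the first and third rows. The same two-point move counts as 100%, 50% or 33.3% depending on where it starts. When the scale is centred on its own neutral point, any subject rated 4 at the first visit has no percentage at all.

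**Group mean.** Assume eight subjects: two with 2 then 4, three with 6 then 4, and three with 4 then 4. These ratings are illustrative and do not come from the documents.

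- Mean absolute change: (2 × 2 + 3 × (−2) + 3 × 0) / 8 = −2/8 = −0.25, the direction of improvement.
- Mean percentage change as numbered: (2 × 100 + 3 × (−33.3) + 0) / 8 = 100/8 = +12.5%, the direction of worsening.
- Mean percentage change reversed: (2 × (−33.3) + 3 × 100 + 0) / 8 = 233.3/8 = +29.2%, where plus now means better.

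The same eight subjects therefore look worse or better on the percentage according to which end of the scale is called 1. The absolute change says slightly better under both codings.

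**A balanced group.** With two subjects 2 then 4, two 6 then 4 and four 4 then 4, the mean absolute change is 0. The mean percentage is (200 − 66.7)/8 = +16.7% under either coding, although plus means opposite things in the two.

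**The case against.** **The SAP does not explicitly require this statistic for these scales.** The sentence on percentage change follows a list of sections that does not include CGI-I. The extension comes through similar analyses, the Appendix 2 titles name no statistics, and no shells exist for the ad hoc outputs. This stands as a limit: the point rests on the natural reading. Nothing in 3.1.1 exempts the two scales, however, and the section is described as the full specification that was followed.

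**A reader might infer that the percentage wrongly shows worsening in a subject who kept an improvement**, for instance 3 in the run-in phase and then 4, which gives +33%. The documents do not support that as a fault of the percentage. With positive scores, each subject's percentage has the same sign as the absolute change, which is +1 here, and the absolute change is kept. SAP 3.1.2 also describes the companion responder comparison as improvement on active treatment against improvement in the earlier phase. On that contrast, 3 then 4 correctly shows less improvement in the active phase, and 2 then 2 correctly shows none either way.

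**A reader might also infer that the sponsor plans to report a percentage improvement in CGI-I as clinical benefit.** Neither document contains or plans such wording.

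**Interpretable outputs already exist.** The responder tables with McNemar's exact test, the by-subject plots and the listings show the ratings properly, and with about eight subjects each rating is visible. This limits the harm but does not give the percentage a meaning.

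**The ad hoc outputs are described as already produced.** Silently deleting a statistic could make the specification differ from what was run. This stands, and the change should be recorded.

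**Conclusion.** The concern holds in a narrow form. On the natural reading of SAP 3.1.1, mean or median percentage change is specified for two ratings on which it is not interpretable. Its size depends on arbitrary numbering, and its group mean can contradict the mean absolute change in direction (−0.25 against +12.5% in the illustration).

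This rests on three things: that similar analyses include the percentage, that the visits are Baseline and End of Treatment (which matters for wording, not for the defect), and assumed ratings for the group example, which shows what can happen and not what did.

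The impact is small. It is confined to descriptive ad hoc Cohort 1 outputs on secondary endpoints. The model contrasts, p-values, responder analysis and primary safety endpoint are unaffected. It is a desirable correction, not an essential one.

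**What to change.** Add one sentence to SAP 3.1.1 stating that percentage change, mean or median, is not presented for CGI-I and OSU CGI-I. Omit it from Tables 14.2.6.1_AH1a and 14.2.11.1_AH1a in the final report. If it has already been tabulated there, mark it as not interpretable and record the change, so that the specification and the outputs still agree.

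Keep the absolute difference, described as the active-phase rating against the run-in-phase rating. Show each visit's rating against 4, as SAP 5.1.2.1 already does in the main analysis. Counts of subjects in each category from 1 to 7 at each visit would be a useful option with so few subjects.

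The cost is one statistic removed or footnoted in two tables, one added sentence and, if wanted, one short count table. No model needs refitting.
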